Aim 2. Aim 2A: To examine whether the reduction in drinking in treatment responders (defined as ≥60% reduction during weeks 9-12) is maintained in a 12-week, phase 2 extension of the initial treatment condition (pbo or dutasteride). This will help to determine the clinical utility of dutasteride as a treatment for AUD, which is a chronic, relapsing disorder. Aim 2B: Increase the number of dutasteride double-blind treated subjects by including in the 12-week phase 2 a cross-over for pbo non-responders to dutasteride and for dutasteride non-responders to naltrexone, a medication with a different mechanism of action compared with dutasteride.

We hypothesize that reductions in drinking for dutasteride responders in phase 1 will be maintained during the 12-week extension period. Additionally, we hypothesize that phase 1 non-responders on pbo will have significant reductions in drinking when crossed over to dutasteride in the second 12-week phase. Further, we expect that a portion of dutasteride non-responders will have significant reductions in drinking when treated with naltrexone, consistent with models of individual genetic and environmental factors producing differences in individual subject responses to medications with different mechanisms of action.

Aim 3. To examine baseline measures of drinking to cope, trait anxiety, perceived life stress, or early life adversity predict dutasteride treatment efficacy, and secondarily, whether a common genetic variation, rs1360780, in the *FKBP5* gene, which encodes a modulator of the intra-cellular steroid hormone signaling system and HPA stress response system, moderates dutasteride treatment response as an interactive effect with these negative affect/life stress measures. We hypothesize that dutasteride treatment benefits

relative to placebo will be greatest for subjects reporting more drinking to cope, greater anxiety, perceived stress or a history of trauma/adversity, particularly for those who are carriers of the *FKBP5* rs1360780 T-allele.

Section 2. RESEARCH STRATEGY

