The proposed study will extend these results by including both sexes and extend our analysis of the relationship of baseline drinking to cope (DTC) and anxiety by adding baseline standardized questionnaires measuring trait anxiety (STAI), early life adversity (ACES), and a perceived stress scale (PSS) which in other settings was more predictive of health care utilization than stressful life event counts (Cohen, Kamarck et al. 1983). Women are expected to have a greater likelihood of elevated DTC, ACES, trait anxiety scores (Smith and Randall 2012) which will enrich our sample in subjects potentially more responsive to dutasteride vs. pbo. We will use separate randomizations for women vs. men and include dichotomized scores for DTC and *FKBP5* risk allele carrier status in our URN randomization to balance for these potential predictors of efficacy. This study may identify easy to score pre-treatment measures such as the CDMQ, ACES, STAI, PSS and genotype that could be clinically useful for making personalized treatment recommendations regarding use of dutasteride to reduce heavy drinking.

2.C. Experimental Approach / Research Plan

2.C.1. General Design: The study will be conducted in the UCHC Clinical Research Center (CRC) clinic. Random assignment to initial treatment group and double-blind conditions will be maintained throughout the study. The study consists of two 12-week phases (**Table 1**), the first being a 12-week parallel-groups comparison of dutasteride and pbo to evaluate the safety and efficacy of dutasteride 1 mg/day in reducing the likelihood of drinking and heavy drinking in a sample of treatment-seeking men and women with AUD. In the second 12-week phase, responders in phase 1 (defined as a ≥60% reduction in SD/wk for weeks 9-12 compared with screening) will continue on their initial medication assignment, while non-responder subjects treated with placebo will cross over to dutasteride, and non-responder subjects treated with dutasteride will cross over to naltrexone. This design maintains double blind conditions in both phases 1 and 2 and is innovative. This design will: i) promote retention and recruitment, as subjects who do not respond to treatment in phase 1 will cross-over to an active FDA approved medication for AUD, ii) provide two comparisons to examine dutasteride efficacy, a between-subjects

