2.C.3.a. Dutasteride is FDA approved to treat prostatic hypertrophy and is a competitive and specific inhibitor of both type I and type II steroid 5α-reductase enzymes with which it forms a stable enzyme complex with very slow dissociation. In humans, type I 5AR is present in the brain, liver, adrenal gland, and adipose tissue and is responsible for onethird of circulating DHT. Type II 5AR is present in the liver and prostate, and is responsible for two-thirds of circulating DHT. For studies of alcohol use, inhibition of type I 5AR may be of particular importance, as type I 5AR, but not type II enzyme, is present in the adult brain (Lephart, Lund et al. 2001) where local generation of neuroactive steroids is thought to occur in addition to peripherally generated neuroactive steroids. The dutasteride dose of 1 mg/day proposed for this study is expected to achieve a >90% inhibition of peripheral type II 5AR and a 60% inhibition of type 1 5AR by 4 weeks for a total reduction in DHT of ≅ 80% by 4 wks based on pharmacokinetic models (Gisleskog, Hermann et al. 1998) and consistent with our observed 80% reduction in 3α-adiol glucuronide at 6 wks in our recently completed initial study in men using this dose. Dutasteride will be purchased commercially and over encapsulated using opaque capsules by the UConn Health Research Pharmacy Service. Pbo will be formulated to match the active medication. Subjects will take one 0.5 mg capsule of dutasteride or matching pbo during the first

treatment visit (baseline study visit 2) and at home on day 2 followed by two capsules daily for either 12 or 24 weeks (depending on treatment response). Similarly, subjects transitioning from placebo or dutasteride based on phase 1 non-response will be given one capsule of medication (dutasteride 0.5 mg or naltrexone 25 mg) during their first phase 2 study visit and day 2 of phase 2 followed by two capsules daily for 12 weeks.

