- 2.C.3.d. Medication Randomization and Drug Accountability: Urn randomization (Stout, Wirtz et al. 1994) will be used to assign subjects 1:1 to dutasteride or pbo for treatment phase 1, balancing for number of DSM5 AUD criteria (2-5 vs.>5), DTC relative to total motives score (0-25% vs. >25%), *FKBP5* genotype (CC vs. T-carrier), current smoking status, and use of medication for treatment of co-morbid psychiatric condition. Separate

randomizations will be done for women and men to ensure balance on these variables in both sex groups. At the end of phase 1, patients who have reduced drinks/week by at least 60% will continue for the second 12 wks on the originally randomized treatment taking 2 capsules per day. Subjects who have reduced drinks/wk by less than 60%, will be informed that they will be transitioning to an active study medication (either dutasteride or naltrexone), and will be interviewed to confirm they have not used opioid medication for 5 days prior which will be verified by urine testing, subjects testing positive for opioids will not be eligible for starting phase 2. For non-responder subjects in the phase 1 pbo arm, the pharmacy will begin dispensing 0.5 mg dutasteride capsules with instructions to take 1 capsule per day for 2 days, then 2 capsules daily for 12 weeks. For subjects in the initial dutasteride arm and reducing less than 60%, the pharmacy will dispense 25 mg naltrexone capsules with the same instructions of 1 capsule for days 1 and 2 followed by 2 capsules each day (50 mg naltrexone per day) to match the dutasteride capsule dosing. Medication vials including any unused medication will brought to each follow-up visit. Unused pill counts will be recorded by the study nurse at each bi-weekly visit and medication use recorded daily by patients on their drink log.

2.C.4. Study Visits:

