For the phase 1 comparison of dutasteride and pbo over time, efficacy analyses will be performed using generalized linear mixed (GLMM) models implemented in SPSS. GLMM incorporates within subject correlation effects important in examination of repeated measures, can incorporate multiple covariates, interactions, random and fixed effects, nonnormal distributions, and is often recommended for designs such as proposed (Mallinckrodt C 2017). Medication group will be treated as a factor and treatment week as a continuous covariate. Sex, smoking status, treatment goal (stop vs. reduce drinking), and use of concurrent medication for co-morbid psychiatric conditions will also be examined as baseline between-subject covariates. Medication group, week, and the other covariates will be modeled as fixed effects, and the intercept will be modeled as random effects. For the outcome HDD/wk a binomial distribution with logit link will be used where the number of HDD during the week will be the numerator and number of observed days the denominator. For the outcome SD/wk a negative binomial distribution with log link will be used. An interaction term between medication group and the week term(s) will be used to evaluate whether the efficacy of dutasteride compared to pbo in reducing drinking varies over time. Interaction effects of sex and treatment condition will also be examined. Pretreatment drinking will be controlled using baseline TLFB drinking data as a covariate. The robustness of results will be evaluated by running the model under three different conditions: 1) modified intention to treat using all available outcome information from subjects with at least 1 post-randomization visit, 2) data from 12-week per protocol completers, and 3) multiple imputation using 10 imputed data sets with weekly drinking and baseline covariates thought predictive of the outcomes or missingness included in the imputation phase.

For aim 2, phase 2 outcomes, the within-subjects analysis will compare drinking during phase 1 against phase 2 for three groups: a) patients responsive to dutasteride in phase 1 and continuing on dutasteride for an additional 12-weeks in phase 2, to examine whether the response is maintained with continued treatment; b) phase 1 non-responders crossed over from pbo in phase 1 to dutasteride in phase 2 to provide a second contrast using an A-B design of the efficacy of dutasteride compared with pbo; and c) phase 1

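### Week-12 non-responders are told their next drug is active, so the placebo-to-dutasteride before-after test is not blind as to active versus placebo and cannot separate drug effect from expectancy

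*Combined protocol and SAP*

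**What the plan says.** **The blinding claim.** Section 2.C.1 (General Design) states: "This design maintains double blind conditions in both phases 1 and 2 and is innovative". Section 2.B (Innovation) also calls the design blinded. Aim 2B gives as one purpose of phase 2: "Increase the number of dutasteride double-blind treated subjects by including in the 12-week phase 2 a cross-over for pbo non-responders".

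**What patients are told.** Under section 2.C.3.d, those who cut weekly drinks by less than 60% "will be informed that they will be transitioning to an active study medication (either dutasteride or naltrexone"). The same sentence introduces an opioid-use interview and urine check.

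**What patients see.** For placebo non-responders, section 2.C.3.d says "the pharmacy will begin dispensing 0.5 mg dutasteride capsules with instructions to take 1 capsule per day for 2 days, then 2 capsules daily". Dutasteride non-responders follow the same pattern with naltrexone capsules. Responders "will continue for the second 12 wks on the originally randomized treatment taking 2 capsules per day". Section 2.C.3.b says that all three capsule types look alike.

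**How the contrast is used.** Section 2.C.1 lists the within-subject test in placebo non-responders as one of two comparisons of dutasteride efficacy. Section 2.C.9.a.2 includes the group "to provide a second contrast using an A-B design of the efficacy of dutasteride compared with pbo" and assigns it a superiority test. Section 2.C.9.b powers it at 90% for a medium effect with 64 patients. The primary outcomes are drinking measures from timeline follow-back interviews.

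**The concern.** For a contrast of dutasteride with placebo, the mask that matters is active versus placebo. Under 1:1 allocation a patient enters phase 1 with an even chance of active drug. At week 12 a non-responder is told that active drug is now certain. For a placebo non-responder, treatment and belief about treatment therefore change together.

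A fall in reported drinking after week 12 could come from dutasteride, from the message, or from both. If the result is then reported as a second, double-blind test against placebo, readers will take it as independent support for the phase 1 finding. The design cannot supply that support.

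**Working it through.** **1. Which masks survive week 12**

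| Item | Status for switchers in phase 2 | Source |
|---|---|---|
| Phase 1 arm | Masked: both non-responder groups get the same message and the same capsule pattern | 2.C.3.d |
| Dutasteride or naltrexone | Masked: capsules look alike | 2.C.3.b |
| Active or placebo | Disclosed | 2.C.3.d |
| Randomized phase 1 comparison | Unaffected: the message comes after it ends | 2.C.1 |

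**2. Can the planned model separate drug from message?** The analysis in 2.C.9.a.2 fits a phase indicator and a second week variable that starts with phase 2. Drug and message change at the same boundary, so both terms carry both effects. A comparator would have to hear the message and stay on placebo. Table 1 has no such group: placebo responders stay on placebo without the message, and dutasteride non-responders hear it but move from one active drug to another.

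**3. Reproducing the plan's power.** Inputs: n = 64 (Table 1, 2.C.9.b) and a paired t-test (2.C.9.b). Alpha of 0.05 and d = 0.4 for a medium effect are carried over from Aim 1, since neither is restated for Aim 2b. Two-sided testing is assumed.

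- Noncentrality = d × √n = 0.4 × 8 = 3.2, with 63 degrees of freedom.
- Power from the noncentral t distribution: 88.3%. Normal approximation: Φ(3.2 − 1.96) = Φ(1.24), about 89%.
- Exactly 90% needs d = 0.41.

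The stated 90% is reproduced to within two points. A one-sided test at d = 0.4 gives 93.6%, and a two-sided test at d = 0.5 gives 97.6%; neither fits as well.

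**4. The same test with no drug effect.** Let expectancy alone shift drinking by a standardized amount d. These values are assumptions; the documents give none.

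| Assumed expectancy shift d | Noncentrality 8d | Chance of a significant result |
|---|---|---|
| 0 | 0 | 5% (2.5% in the direction of less drinking) |
| 0.1 | 0.8 | 12% |
| 0.2 | 1.6 | 35% |
| 0.3 | 2.4 | 66% |
| 0.4 | 3.2 | 88% |

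The critical t is about 2.00, so an observed standardized change of 2.00 / 8 = 0.25 is enough for significance. The last row equals the power in step 3, because the test treats an expectancy shift and a drug effect of the same size alike.

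**The case against.** **Much stays masked.** A reader might infer that phase 2 is simply unblinded, or that Aim 2B yields no blinded dutasteride exposure. The documents do not support that: switchers know neither their phase 1 arm nor which active drug they now take. Nor is the phase 1 efficacy result touched. Both limits stand and narrow the point.

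**The capsule count.** One might argue that the drop to one capsule breaks the blind by itself. It lasts two days, repeats the start of phase 1, and is the same for both switching groups. Once patients have been told, it adds little.

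**Interviewers.** It is tempting to say that the staff taking drinking reports also know of the switch. That is inference: section 2.C.3.d does not say who informs the patient, and section 2.C.4.c does not tie the interview to that person.

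**Safeguards exist.** PEth is a secondary outcome at the end of each phase. Daily telephone drinking reports cover weeks 9-12 and 21-24, and the MED-Q records believed assignment. These bear on misreporting and belief. They do not remove a real change in drinking driven by expectancy, and section 2.C.6.b.3 ties the MED-Q to no efficacy analysis.

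**The percentages are illustrative.** They come from the power-section t-test, not from the planned mixed model. The restricted-period analysis uses weeks 21-24, which begin eight weeks after the switch, so the shift would also have to persist. Any other non-drug change would give the same figures in an uncontrolled comparison. They should not be read as an estimated false-positive rate.

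**The disclosure has a purpose.** Section 2.C.1 values the move to active medication for recruitment and retention, and some switchers are starting an opioid antagonist. This weighs against insisting that the message be withdrawn. It does not support the double-blind label.

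**Conclusion.** The point holds in a limited form. The double-blind claim for phase 2 contradicts section 2.C.3.d on active-versus-placebo status, the one mask that a placebo-to-dutasteride contrast needs. That contrast cannot attribute a fall in drinking to dutasteride rather than to expectancy. The size of any expectancy effect is unknown from the documents. Under assumed shifts of d = 0.1 to 0.3 lasting into the analysis window, with no drug effect, a significant result would occur about 12% to 66% of the time instead of 5%.

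A reader might also infer that different week-12 wording would cure the problem. The documents do not support that. Patients keep daily drinking records and review their drinking at each medical management session, so anyone who knows the 60% rule could often infer non-response and hence a switch. The consent pages are not in the public document, so what patients know beforehand cannot be checked. And without a concurrent control the comparison stays uncontrolled whatever is said.

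**What to change.** 1. In Aim 2B and sections 2.B and 2.C.1, limit the phase 2 blinding claim to drug identity and phase 1 arm, and state that switchers are told their new medication is active.
2. In sections 2.C.1, 2.C.9.a.2 and 2.C.9.b, describe the placebo non-responder analysis as an uncontrolled before-after comparison, open as to active status. Do not present it as a blinded second test of efficacy against placebo.
3. Report beside it the change in PEth between weeks 12 and 24 and the MED-Q beliefs at the end of each phase. Note that these address misreporting and belief, not a real expectancy-driven change.

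These steps cost a short wording amendment and two extra summaries of data already collected.

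Optionally, the sponsor may consider making the week-12 wording and capsule counts uniform for responders and switchers, with no change to any active dose and with the opioid-safety information and checks kept as written. This would reduce the bias, not remove it, and may cost some retention. It is a trade-off for the sponsor, and items 1 to 3 do not depend on it.

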We recently completed the first RCT of **Dutasteride for the reduction of heavy** drinking in men. Results support further examination of dutasteride as a treatment option for AUD. In total 189 treatment seeking men were enrolled of which 24 were screen failures and 23 failed to return for the baseline visit leaving 142 subjects randomized to medication (dutasteride n=74). Seven subjects did not return after the baseline randomization visit providing a modified intention to treat sample of 135 subjects (68 dutasteride and 67 placebo) who provided drinking data post-randomization. One hundred seven subjects completed the entire 12-week treatment. The mean number of treatment weeks completed were not different between arms (dut 10.2 vs. pbo 10.7). 3α androstanediol glucuronide levels were decreased by 80% in the dutasteride group at both 6 and 12 weeks vs. 0% in pbo treated subjects confirming the anticipated pharmacological effect for our study design. There were no significant differences between groups (dutasteride vs. pbo) for measures of alcohol consumption during the 60-days prior to screening including the number of standard drinks (SD) per week (48.8 vs. 47.3), number of heavy drinking days (HDD, 5 or more drinks for men) per week (5.2 vs. 5.2), or abstinent days per week (0.67 vs. 0.62). While the dutasteride group were more likely to have had a prior episode of treatment for alcohol use (59% vs. 40%, p=0.03) the number of DSM-IV AD criteria did not significantly differ between groups (4.3 vs. 4.0).

[figure not shown]
Safety. There were no study related serious adverse effects. The proportion of subjects exposed to study medication who reported at least one non-serious adverse

[figure not shown]
effect was not significantly different for the dutasteride vs. pbo groups 71.6% vs. 67.1% similarly, the number of side effects per subject was not different between dutasteride and placebo groups, 1.36 ± 1.46 vs. 1.03 ± 1.10 . Adverse events that were reported by more patients in the dutasteride compared with the placebo arm included stomach discomfort (16.4% vs. 4.5%, p=0.04) and reduced libido (9.0% vs. 0%; p=0.03). More subjects in the dutasteride arm (n=4) than the pbo arm (n=1) stopped medication due to side effects. Beck Depression Inventory scores were low in both treatment arms at baseline (10.4 dut vs. 7.5 pbo) and reduced to a similar degree during the 12-week treatment (-3.3 dut vs. -2.4 pbo, t=0.6; p=0.5).

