comparison in phase 1 and a within-subjects test in phase 2 for patients treated with pbo in phase 1 and dutasteride in phase 2, iii) allow evaluation of whether reductions in drinking are maintained with ongoing treatment for phase 1 dutasteride responders, and iv) provide preliminary data on whether dutasteride non-responders show reductions in drinking when crossed over to naltrexone, an established medication for AUD with a different mechanism of action compared with dutasteride.

Three and six-month follow-up visits following the completion of the 24-week treatment phase will evaluate the durability of treatment effects, allow measurement of the degree to which dutasteride effects on 5AR inhibition have been reversed following 12- or 24-week exposures and to maintain contact with female participants to remind them of the importance of effective contraception for 6 months following treatment.

Table 1. Expected Patient Distribution for Phase 1 and 2.

Phase 1	Phase 1	Phase 1	Phase 2	Phase 2 Statistical contrasts
Treatment	Statistical	Expected Tx	Treatment	
	contrasts	response groups		
Dutasteride n=95 (grp A)	Between-subject contrasts using GLMM Dut vs. Pbo for DVs HDD/wk and SD/wk;.	Dut-R (wk 9-12 Response n=40) Dut-NR (wk 9- 12 Non-Response n=40)	Dut-R dutasteride Dut-NR naltrexone	Within-subject interrupted time series regression using mixed models. Dut-R: Is dut response maintained? Dut-NR: Do dut NRs respond to naltrexone?
	Moderating			
Pbo n=95 (grp B)	effects of genotype, baseline state vs. trait anxiety, perceived stress and interaction with FKBP5 genotype	Pbo-R (wk 9-12 Response n=16) Pbo-NR (wk 9- 12 Non-Response n=64)	Pbo-R pbo Pbo-NR dutasteride	Pbo-R: insufficient sample for statistical comparison. Pbo-NR: Do pbo NRs respond to Dut?

Phase 1 response ≥ 60% reduction SD/wk for wk 9-12 vs baseline (current study 49% response rate for dut vs. 20% pbo). dutasteride 1 mg/day; naltrexone 50 mg/day.

2.C.2. Patients: Drinkers who want to reduce or stop drinking will be recruited using advertisements in radio and print media, by posting/distributing recruitment materials in community settings, informational mailings to area clinicians and by referral from UConn Health medical and dental clinics in at our main campus in Farmington CT together with

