Relevant portions of the Structured Clinical Interview for DSM-5 will be administered by a research assistant to exclude subjects with active major mental illness or current moderate to severe substance dependence other than alcohol, caffeine or tobacco. A Timeline Follow-Back (TLFB) interview will be performed to collect daily alcohol consumption for the 90 days prior to screening. Blood and urine samples will be taken for routine clinical laboratory evaluations, drug screening, DNA extraction and for measurement of the alcohol use biomarker phosphatidylethanol (PEth, which will be used as a secondary measure of drinking), the steroid metabolite 3α -diolG to monitor 5AR inhibition and ACTH and cortisol to examine for the effects of dutasteride on the ACTH/cortisol ratio. Efforts will be made to schedule individual subjects at the same time of day for each of their visits involving blood draws to reduce the within subject effects of diurnal variation in hormone levels (based on our prior studies, a majority of our subjects are anticipated to be employed with consistent times requested for study visits). Finally, subjects will be provided a stool sample collection kit and instructed on its use at home for obtaining stool samples to be returned at Visit 2. Stool samples will be collected at baseline and end of treatment phase 1 and archived at -80C for batch processing to catalog each subjects gut microbiome via DNA sequencing as part of a Center pilot project in order to contrast the gut microbiome sampled at baseline between subjects who reduce or do not reduce their drinking during phase 1 of the study. Prior reports suggest that gut colonization with proinflammatory microorganisms may be associated with greater difficultly in reducing drinking (Leclercq, Matamoros et al. 2014, Leclercq, de Timary et al. 2017, Leclercq, Starkel et al. 2018). We will also contrast the change in the gut microbiome comparing baseline and endpoint stool samples as a function of reduction in alcohol use. We have had good acceptance rates in pilot use of this stool collection method in other clinical studies. Subjects will be paid a nominal amount of money in consideration of their time and inconvenience for visits beyond the baseline visit (e.g., visits 3-16) as well as for completing the IVR daily calls. Total potential compensation is \$620 for completing all 16 visits and all IVR calls.

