2.C.8 Exploratory microbiome analysis Leclercq et al (Leclercq, Matamoros et al. 2014, Leclercq, de Timary et al. 2017) have reported that as many as 40% of alcohol dependent subjects may harbor pro-inflammatory gut microbiota contributing to increased gut permeability which was associated with higher anxiety and alcohol craving after 3 weeks of abstinence. Our hypothesis is that participants with higher levels of pro-inflammatory gut microbes at baseline will have less success in reducing drinking. Stool samples will be collected by participants at home and transported to the CRC in a small cooler with freezer packs. Samples will be stored at -80C until batch processed. DNA will be prepared from stool samples and used for metagenomics whole genome shotgun sequencing of microbial DNA. This method allows species and strain level identification of the gut microbiome. Analysis of sequence data and comparison of strains by treatment response will be done by [name] Assistant Professor of Medicine at UConn Health who is an experienced investigator in molecular characterization of human microbiomes. Correlations of the relative abundance of microbes in baseline stool samples with participant success and in reducing weekly drinking will be examined. We will also examine change in microbiome between baseline and endpoint as a function of change in drinking.

2.C.9. Data Analysis:

2.C.9.a.1. Safety: Safety will be analyzed using categorical outcomes, defined by the type and severity of adverse effects. Summary measures of adverse effects (AEs) will be developed by organ system from the SAFTEE adverse event checklist and will be compared for patients receiving dutasteride or pbo using χ^2 analysis in phase 1 and

comparing patients switched to dutasteride vs. naltrexone in phase 2. Comparisons will be conducted on 1) the proportion of patients in each of the comparison groups who report AEs, 2) the proportion of patients in each of the comparison groups who report moderate-to-severe AEs, and 3) the proportion of patients in each comparison group who discontinue treatment due to AEs. Individual AEs that occur in \geq 5% of patients in either medication condition will be examined using χ^2 analysis.

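### The exploratory microbiome change analysis has no treatment-arm term, so about a third of any direct dutasteride effect on the gut would be read as an effect of drinking less

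*Combined protocol and SAP*

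**What the plan says.** The microbiome work is described in two places: section 2.C.4.a (Visit 1), as part of a Center pilot project, and the section headed "2.C.8 Exploratory microbiome analysis". Stool is collected before treatment and again at the end of phase 1, after 12 weeks on dutasteride or placebo.

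Two kinds of analysis are planned.

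- **Baseline samples.** Section 2.C.4.a will "contrast the gut microbiome sampled at baseline between subjects who reduce or do not reduce their drinking during phase 1 of the study". Section 2.C.8 adds: "Correlations of the relative abundance of microbes in baseline stool samples with participant success and in reducing weekly drinking will be examined".
- **Change from baseline to week 12.** Section 2.C.4.a: "We will also contrast the change in the gut microbiome comparing baseline and endpoint stool samples as a function of reduction in alcohol use". Section 2.C.8: "We will also examine change in microbiome between baseline and endpoint as a function of change in drinking". That section also announces "Analysis of sequence data and comparison of strains by treatment response".

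Subjects are grouped or ordered by drinking outcome throughout. Neither section mentions treatment arm, stratification by arm, or any covariate. By contrast, the phase 1 efficacy model in 2.C.9.a.2 includes medication group and baseline drinking, and the aim 3 models include medication condition.

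**The concern.** Arm is randomised, and the trial expects it to reduce drinking. It therefore lies upstream of the quantity that the change analysis treats as its explanatory variable. If dutasteride also reaches the gut by a route other than drinking, the unadjusted association between gut change and drinking change mixes the two. The better the drug works on drinking, the more unequal the arm mix between those who cut down and those who do not, and the larger the mixing.

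What is at stake is interpretation: a taxon shifted by the drug alone could be reported as one that responds to reduced drinking. No primary or secondary efficacy result depends on this.

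**Working it through.** **Inputs.** Table 1 expects 40 responders and 40 non-responders on dutasteride ("Dut-R (wk 9-12 Response n=40" is the first of these), and 16 and 64 on placebo. Its footnote gives response rates of 49% and 20%. Section 2.C.9.b gives 80 phase 1 completers per arm.

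**Reproducing Table 1.** 0.49 × 80 = 39.2 and 0.51 × 80 = 40.8 (stated 40 and 40); 0.20 × 80 = 16 and 0.80 × 80 = 64 (stated 16 and 64). The table is built on completers; 95 randomised per arm would give 46.6 and 19 responders.

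**Arm mix by response.**

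- Responders: 40 / (40 + 16) = 71.4% on dutasteride.
- Non-responders: 40 / (40 + 64) = 38.5%.
- Difference: 0.330. With the unrounded counts it is 39.2/55.2 − 40.8/104.8 = 0.321, so rounding matters little.

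**Bias.** Let dutasteride shift a taxon by d (in SD units within an arm) and let drinking have no effect. The expected unadjusted difference between responders and non-responders is 0.330 × d. The documents give no value for d, so a range is shown.

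**Error rate.** The contrast has sampling error √(1/56 + 1/104) = 0.166. Mixing arms within each response group also widens the spread that the test uses. The added variance is v × d², where v = [56 × 0.714 × 0.286 + 104 × 0.385 × 0.615] / 160 = 0.225. The estimated standard error is then 0.166 × √(1 + 0.225 d²). For d = 1.0 this is 0.183, so the test statistic centres on 0.330 / 0.183 = 1.80 with SD 0.166 / 0.183 = 0.90. It exceeds the 5% critical value of 1.975 about 42% of the time. Simulation agrees:

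| Assumed d (SD) | Bias without arm (SD) | Error, Table 1 counts fixed | Error, responder counts varying around Table 1 rates | Error with arm in the model |
|---|---|---|---|---|
| 0 | 0 | 5% | – | 5% |
| 0.3 | 0.10 | 9% | 9% | 5% |
| 0.5 | 0.16 | 15% | 16% | 5% |
| 1.0 | 0.33 | 42% | 43% | 5% |

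The unadjusted columns assume that all 160 completers give both samples. With half as many pairs and the same arm mix, they fall to about 7%, 10% and 22%. The bias is unchanged.

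**Cost of the arm term.** The correlation between arm and response is (40 × 64 − 40 × 16) / √(80 × 80 × 56 × 104) = 0.314. Variance inflation is 1 / (1 − 0.314²) = 1.11. Power for a true drinking effect of 0.5 SD falls from 85% to 82%.

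**The case against.** The strongest reply is that the harm is wholly conditional. The documents show no dutasteride effect on the gut microbiome. A reader might cite the first trial's adverse events in 2.B.2, "stomach discomfort (16.4% vs. 4.5%, p=0.04", but that is a symptom and not evidence of microbial change; the upper value of 1.0 SD has no support in the documents. This stands: the plan leaves an alternative explanation open, and no bias has been shown.

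Pooling is inferred. The text is silent on covariates and does not say that arm will be left out. This also stands, although two descriptions that define groups by drinking outcome alone are most plainly read as pooled.

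The 71% and 38% rest on the 60% cut-off. Section 2.C.8 refers to treatment response, which the protocol defines that way, but the other wording (reduce or not, change in drinking) sets no cut-off. Another split or a continuous measure would give a different imbalance. Its direction still follows from the assumed efficacy.

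A reader might extend the point to the baseline analysis. The documents do not support that. Those samples precede dosing, so no drug effect on the gut can enter them. The stated hypothesis is also predictive: a taxon that forecasts success is a predictor even if it also marks heavier drinking. Adjusting for screening drinking there is a preference.

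Finally, the work is labelled exploratory, lies outside Aims 1 to 3 and the listed outcomes, and has no stated significance level; the 5% per taxon is used here only as a yardstick. That limits the severity. It does not remove the risk of a wrong reading.

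**Conclusion.** The point holds for the change analysis only, as a low-severity improvement. Followed as written, that analysis would attribute about one third (0.33) of any direct drug effect on the gut to drinking less. This assumes Table 1's expected counts, the 60% response definition, no true drinking effect on the taxon, and a direct drug effect that remains hypothetical.

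A simpler calculation, which uses the standard error of 0.166 and ignores the extra within-group spread, would suggest error rates of 17% and 51% at 0.5 and 1.0 SD. Those are too high: the supportable figures are about 16% and 43%, with 9% at 0.3 SD, and all three are upper values because they need complete paired sampling. Nothing here bears on the primary comparison of dutasteride with placebo.

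**What to change.** In section 2.C.8, state that the analysis of microbiome change will include randomised arm as a covariate, that the association with drinking change will also be reported within each arm, and that any conclusion about drinking will rest on the arm-adjusted estimate. Arm does not lie on a path from drinking to the gut, so adjusting for it does not remove a real drinking effect.

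Arm is already recorded, so the change costs a sentence of text and the small loss of precision shown above. For the baseline analysis no change is needed; screening drinks per week could be offered as an optional sensitivity covariate.
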